## **8.3** Radiological Studies

Patients, who respond (complete remission [CR] or partial remission [PR]) to therapy, have pseudo-progression or have long-term stable disease (SD;  $\geq$  six [6] cycles) on protocol therapy will be centrally reviewed at The Hospital for Sick Children. CRO will notify The Hospital for Sick Children of any patient requiring central review. The Hospital for Sick Children will then request that the treating institution forward the requested images for central review. The central image evaluation results will be entered for data analysis.

The images are to be sent (preferably CD) to The Hospital for Sick Children.

## 8.4 Biological and Companion Biomarker Studies

Please refer to the *Lab Manual* for the instructions on tissue and blood collection and shipment arrangements. All eligible patients will be asked to consent to parallel biological and companion biomarker studies to further advance our knowledge of paediatric patients with hypermutant cancers being treated with nivolumab. With patient consent, available data from locally REB approved biobanks may be added and used in conjunction to data obtained in this clinical trial to enhance our understanding of the mechanisms at play. All patient information will be de-identified in accordance with REB approval and patient consent, and any information obtained as part of the study will not be shared/ divulged reciprocally.

#### **8.4.1** Tumour Tissue

<sup>17These assessments for C1D1 pre-dose do not need to be repeated if these were done for baseline within seven (7) days prior to C1D1.

<sup>18 Assessments are to be done on days CXD1 ±2 days or CXD15 ±2 days on the day of and prior to nivolumab administration.

<sup>19 Samples may be taken up to 7 days prior to C1D1 dosing.

<sup>20 30 days after last dose.

<sup>21 Every 3 months for 1 year.

<sup>22 Unlike the *Companion Biomarkers*, if the CXD1 of cycle drug administration is delayed or omitted, all *Clinical Assessments* and *Laboratory/ Imaging Investigations* (and their respective windows) should adjust to the new CXD1, reflecting the patient's status prior to the upcoming drug administration. Please see respective footnotes above for details for changes to the *Companion Biomarker* assays.

In order to be included in **Part I** of the study, patients must have at minimum neoplastic specimen available as specified in the *Lab Manual*. With patient consent, said specimens will be assayed using NGS in a specific CLIA–certified laboratory approved by the Study Chair or Co-Chair to assess TMB for eligibility purposes. If this tissue is not available, but a TMB report from the specific CLIA–certified laboratory approved by the Study Chair or Co-Chair is already available, this information can be used for eligibility purposes. Whenever possible, both a fresh, formalin-fixed, paraffin-embedded tumour tissue sample and a fresh frozen tumour tissue sample are preferred to be used for TMB, other *Companion Biomarkers* studies and future biomedical research outlined above. Fresh frozen tissue is highly recommended for affiliated biomarker study once on trial. Please refer to *Lab Manual* for the detailed instructions for submission of the tissues.

In addition, all patients are also highly encouraged to submit paraffin embedded tumour sample to assess for MMR protein expression loss by IHC in a CLIA-certified environment for genes including, but not limited to MLH1, MSH2, MSH6, and PMS2. These results may also be used for inclusion to **Part II**, Cohort C (see above for details). As part of the *Companion Biomarker* studies in **Part II**, immune-related markers including but not limited to CD3, CD4, CD8, CD68, PD-1, and PD-L1 expression will also be assessed by IHC.

In the event a patient requires a biopsy or surgery and tumour tissue is removed while on study, tissue will be requested for biological analyses.

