# 2.3 Exploratory/Biology Objectives

- 1. To explore associations between TMB and response to nivolumab therapy.
- 2. To discover biomarkers predicting response of hypermutant cancers undergoing PD-1 blockade by investigating tumour neoantigen formation, specific T-cell receptor rearrangements (TCRR) of peripheral lymphocytes and tumour infiltrating lymphocytes (TILs), as well as a detailed characterization and activation of the immune infiltrations including the TILs.
- 3. To explore the use of minimally invasive methods to monitor and predict response to immune checkpoint inhibition in hypermutant cancers by investigating TCRR, phenotypic profiling of specific immune cells and their activation as a prognostic factor and variances throughout treatment as a response to therapy. As well, to investigate circulating tumour DNA (ctDNA) from serial peripheral blood samples as a surrogate marker of response.

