- $^8$  Women of childbearing potential (WOCBP; and those with Tanner stage of ≥ 3) must have a negative pregnancy test every 4 weeks. During the **Part II** screening window (-14 days), WOCBP must have a negative serum pregnancy test. WOCBP must have a negative serum or urine pregnancy test (minimum sensitivity 25 IU/L or equivalent units of HCG) within 24 hours prior to the start of nivolumab administration and must be willing to adhere to effective contraception during treatment and for 5 months after the last dose of nivolumab. Males who are sexually active with women of childbearing potential must be willing to adhere to effective contraception during and for 7 months after the last dose of nivolumab. Abstinence is an acceptable method of birth control. Additional pregnancy tests (serum or urine) should be obtained during treatment in accordance with institutional guidelines.
-  If patients have Grade 4 neutropenia then CBCs should be checked twice weekly or as clinically indicated until recovery to Grade 3 or until meeting the criteria for removal from the study.
-  Biochemistry includes: sodium, potassium, calcium, chloride, phosphate, magnesium, serum creatinine, BUN (urea), bilirubin (conjugated/unconjugated or total), ALT and AST.
-  Free T4 should also be measured for patients with an abnormal TSH level. Guidance on the management of patients who develop hypothyroidism is included in *Section 7.10*. TSH will be assessed at end of each cycle, within 3 days prior to the next cycle.
-  During the study, disease evaluations will be done at end of cycle 1 (window of -7 days) and every two (2) months (window of -7 days) as per *Section 10* applicable response evaluation criteria. Tumour disease assessments will also be done at end of treatment visit (window of +/-7 days) and once every three (3) months (window of +/-14 days) during follow-up for 1 year. Tumour disease assessments during follow-up may be performed at referring hospital. Evaluations required will depend on patient diagnosis. For patients with solid tumours, CT or MR imaging of appropriate sites is mandatory. For patients with leukaemia, BM evaluation is adequate.

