-  Recommended for patients with confirmed or suspected CMMRD only; not mandatory. Regardless of study participation, patients with confirmed or suspected CMMRD should undergo regular tumour surveillance according to published guidelines (see *Section 8, Table 4*, Tabori, 2017).
-  Tissue provided in **Part I** may be used for *Companion Biomarker* studies with patient consent. Whenever possible, additional samples will be obtained for biological analyses in the event that a patient requires surgery/a biopsy after starting treatment and cancerous tissue is removed. Tumour will be only biopsied/ surgically removed for medical/ diagnostic purposes and not specifically for the purposes of the study. When possible (with patient consent), please contact Study Chair or Co-Chair as well as refer to *Lab Manual* prior to surgery/ biopsy acquisition while on study to facilitate time and preservative-sensitive sample processing.
- Blood for circulating tumour DNA (ctDNA) is required at baseline, at the end of Cycle 1, but prior to C2D1 dose (window -7 days from C1D28), every two (2) months at the end of the cycle prior to the subsequent CXD1 dose (window -7 days from CXD28 of the previous cycle) during the study, at the end of study visit and every 3 months subsequently (window ± 14 days) during follow up for 1 year (i.e. at the times of disease re-evaluation). To be extracted and processed immediately on same day (as per *Lab Manual*). All *Companion Biomarker* assays must be performed approximately 4 weeks after CXD1, irrespective of any dose omissions or delays. The results of these assays should reflect the effect of the two former doses, not the status at CXD1. All attempts to compile blood draws to visit dates prior to drug administration should be made.
- Blood extracted PBMCs for T-cell functional studies are required at baseline, on Cycle 1, Day 15 (C1D15; window –7 days), at the end of Cycle 1, but prior to C2D1 dose (window -7 days from C1D28), every month at the end of the cycle, prior to the subsequent dose

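### A late or omitted day-1 dose moves the tumour scan off its two-monthly schedule and, at that assessment, away from the ctDNA sample meant to be read against it

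*Protocol*

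**What the plan says.** All of the scheduling text belongs to the Part II calendar in Protocol Section 8.2. Disease assessment is a row in its Laboratory/Imaging block, and the heading of that block carries footnote 22.

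- **Footnote 12 (scans):** "disease evaluations will be done at end of cycle 1 (window of -7 days) and every two (2) months", with a window of -7 days. It does not say what happens when a dose is late.
- **Footnote 22 (delays):** "if the CXD1 of cycle drug administration is delayed or omitted", the clinical assessments and the laboratory and imaging investigations "and their respective windows) should adjust to the new CXD1". The footnote contrasts this with the companion biomarkers and makes no exception for tumour imaging. Its stated reason is that the findings should show the patient's condition before the coming dose.
- **Footnote 15 (ctDNA):** the sampling times are glossed as "i.e. at the times of disease re-evaluation". The same footnote then requires the assays "approximately 4 weeks after CXD1, irrespective of any dose omissions or delays", because they should reflect the two preceding doses.
- **Section 2.3:** an exploratory objective is to study "circulating tumour DNA (ctDNA) from serial peripheral blood samples as a surrogate marker of response".
- **Length of a delay:** Section 5.3 requires permanent discontinuation once a delay exceeds six weeks. Section 6.2 removes a patient when a non-haematological toxicity needs a delay of more than seven days.

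**The concern.** Footnote 22's reason suits pre-dose safety checks: blood counts and chemistry should be current when the drug is given. An efficacy scan has a different purpose. PFS runs from first dose (synopsis, efficacy criteria), so a later scan gives a later date to any progression that is found by scan. Section 5.2 lists mainly drug-related adverse events and laboratory abnormalities as grounds for delay. Patients with toxicity would therefore be imaged on a different rhythm from those without, and part of any difference in their PFS would come from the schedule.

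The ctDNA objective relies on each sample being read against the scan it accompanies. Under footnote 22 the scan moves; under footnote 15 the sample does not. A later analysis cannot recover a scan that was not taken on time or a sample that was not paired.

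**Working it through.** The protocol states no figure that depends on this point, so there is none to reproduce. The check is schedule arithmetic plus one illustrative calculation.

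**Inputs.** Scans at week 4 and then every 8 weeks (footnote 12, taking two months as two 28-day cycles, an assumption). Scans are therefore due at weeks 4, 12, 20, 28 and 36, coinciding with C2D1, C4D1 and so on. One day-1 delay of *d* weeks, with *d* up to 6 under Section 5.3 or about 1 under Section 6.2.

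**Scan dates under footnote 22.** New date = planned date + *d*. If the delay falls at C4D1, that interval becomes 8 + *d*. The gap to ctDNA at that assessment is *d*, because footnote 15 does not move the sample.

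| Delay *d* | First scan if C2D1 slips | Second scan if C4D1 slips | Interval before it | Scan-to-ctDNA gap |
|---|---|---|---|---|
| 0 | week 4 | week 12 | 8 weeks | 0 |
| 1 week | week 5 | week 13 | 9 weeks | 7 days |
| 2 weeks | week 6 | week 14 | 10 weeks | 14 days |
| 4 weeks | week 8 | week 16 | 12 weeks | 28 days |
| 6 weeks | week 10 | week 18 | 14 weeks | 42 days |

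Later scans keep the same shift from first dose. If CXD1 in footnote 15 means the actual dose date, the ctDNA gap returns to zero at the next assessment. If it means the nominal date, the gap persists.

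**Detection lag within one stretched interval.** For a progression falling uniformly in the interval, mean lag = interval / 2: 8/2 = 4 weeks, 10/2 = 5, 12/2 = 6, 14/2 = 7.

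**Detection lag over a patient's whole course.** Time to progression was simulated as exponential, with true medians of 8, 13 and 26 weeks (assumed, not from the protocol) and a single C2D1 delay.

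| C2D1 delay | Mean lag in weeks, median 8 | median 13 | median 26 |
|---|---|---|---|
| 0 | 3.77 | 3.86 | 3.93 |
| 1 week | 3.83 | 3.89 | 3.95 |
| 2 weeks | 3.98 | 3.98 | 3.99 |
| 6 weeks | 5.18 | 4.76 | 4.40 |

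A six-week delay raises the mean lag from 3.8-3.9 to 4.4-5.2 weeks. A one-week delay adds less than 0.1 week.

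**Confirmation scans.** Section 10.2.7 wants the assessment after an unconfirmed progression within eight weeks. A routine scan due 8 weeks later and pushed back by 6 would fall at 8 + 6 = 14 weeks, outside that limit unless an extra scan is ordered.

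**Schedule fixed to C1D1.** Scans stay at weeks 4, 12, 20, 28 and 36. The longest interval is 8 weeks, and with ctDNA drawn at the scan visit a delay adds no gap.

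**The case against.** **The trigger is narrow.** A reader might infer that every dose delay moves the scan. Footnote 22 names only a delayed or omitted day-1 dose; a late day-15 dose matters only if it pushes back the next day 1. Scans are due in the last week of the cycle, so some will already be done when a delay is decided. Both points stand.

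**The long delays may be rare.** Section 6.2 removes patients whose non-haematological toxicity needs more than seven days' delay, and also those with many attributable Grade 3-4 toxicities. Once off treatment they follow the end-of-treatment and three-monthly scans in footnote 12, outside footnote 22. On that reading the shift is about the size of the existing window. This limits the size, but Section 5.3 says otherwise and the two are not reconciled.

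**PFS is not always dated at a scan.** Death is an event. Section 10.9.2 dates clinical progression of a CNS tumour at neurological decline, and Section 10.14 allows leukaemia progression on blood counts or clinical evidence. PFS is secondary, in a single arm, with no decision rule. This stands: the effect is confined to scan-detected events.

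**The ctDNA rule is a deliberate exception.** Footnote 15 can be read as a nominal schedule followed by an express rule for delays, with a reason given. That is fair, and it makes outright self-contradiction too strong a charge. The result is unchanged: in a delayed cycle the sample no longer coincides with the assessment it is meant to track.

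**Conclusion.** The point holds in limited form. When a day-1 dose is late or omitted, footnote 22 displaces the two-monthly scan interval, makes it depend on delays caused mainly by toxicity, and separates scan from ctDNA at that assessment. The upper bound is a 14-week interval and a 42-day gap, reached only with a six-week delay under Section 5.3. Under the seven-day rule of Section 6.2 the effect is about one week. The two sections must be reconciled; this review does not say which is right.

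Two stronger readings are not supported. A reader might take the rise in lag from 4 to 7 weeks as the shift in PFS. It applies only to events inside one maximally stretched interval; under the assumed exponential model, a six-week C2D1 delay adds between about 0.5 and 1.4 weeks on average (4.40 - 3.93 and 5.18 - 3.77), in delayed patients only. A reader might also infer damage to the primary analysis. The Simon rules in Section 11 count responders and are numerically unchanged, and Section 10.4.1 takes best response through the end of treatment. Only the timing of response detection moves.

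This is a cheap improvement to a secondary and an exploratory endpoint and should be made.

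**What to change.** 1. **Footnote 22:** exempt the disease assessment row. Leave pre-dose clinical and laboratory safety checks tied to the actual dose.
2. **Footnote 12:** state that tumour assessments run on calendar time from C1D1 (end of week 4, then every 8 weeks, with the stated window) whatever the dose delays or omissions.
3. **Footnote 15:** state that the ctDNA sample used as a response surrogate is drawn at the same visit as the scan.
4. **Footnote 16:** say whether the PBMC draws follow the scan or stay linked to dosing.
5. **Sections 5.3 and 6.2:** reconcile the two limits on delay, since they determine how large the effect can be.

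Items 1 to 4 are edits to footnotes and add no scan beyond the stated two-monthly frequency. There are two downsides. A scan may fall between doses. After a delay, some ctDNA samples will no longer be exactly four weeks after CXD1, which gives up part of footnote 15's stated purpose and may separate them from the PBMC draws.

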#### **8.4.2** Blood Tissue

All patients are required to submit blood sample for DNA and RNA gene sequencing to assess for RRD syndromes as well as other biomarker assays.

All patients are required to submit blood sample to establish a lymphoblast cell line.

All patients are required to submit serial blood samples at baseline and during treatment to assess for the T-cell fraction enrichment (from PBMCs) in response to nivolumab, and circulating tumour DNA (from plasma) all extracted and processed immediately same day. Please refer to *Lab Manual* for the detailed instructions for submission of the tissues.

#### 9. EXPERIMENTAL AGENT

#### 9.1 Nivolumab

BMS-936558, MDX1106, ONO-4538, anti-PD-1, NSC#748726, Opdivo ®.

## 9.2 Structure and Molecular Weight

Nivolumab is a soluble protein consisting of 4 polypeptide chains, which include 2 identical heavy chains consisting of 440 amino acids and 2 identical light chains. Molecular weight is 146 221 Daltons.

## 9.3 Supply

Nivolumab will be supplied by Bristol-Myers Squibb (BMS) and distributed directly by BMS or via an approved supplier.

#### 9.4 Formulation

The agent is a clear to opalescent, colorless to pale yellow liquid, with light (few) particulates. It is available in a 100 mg/10 mL vial containing a sterile, non-pyrogenic, single-use, isotonic aqueous solution formulated at 10 mg/mL in sodium citrate, sodium chloride, mannitol, diethylenetriamine pentacetic acid (pentetic acid) and polysorbate 80 (Tween® 80) to a pH of 6.0. A small amount of overfill (0.7 mL) is included with each vial to account for VNS (vial, needle, syringe) loss. The 10-mL type I flint glass vials are stoppered with butyl rubber stoppers and sealed with aluminum seals.

## 9.5 Storage

Nivolumab vials for injection must be stored as per conditions outlined in Investigator Brochure.

## 9.6 Solution Preparation

Nivolumab injection can be infused undiluted (10 mg/mL) or diluted with 0.9% Sodium Chloride Injection, USP or 5% Dextrose, USP to a final concentration of 1 - 10 mg/mL. Vial

contents from different lots should not be mixed in the same infusion. Please refer to the current Investigator Brochure for details.

## 9.7 Stability

The administration of undiluted and diluted nivolumab must be completed within 24 hours of preparation. If not used immediately, the infusion solution of nivolumab injection prepared for dosing may be stored for up to 24 hours in a refrigerator at 2°-8°C (36°-46°F) and a maximum of 8 hours of the total 24 hours can be at room temperature (20°-25°C, 68°-77°F) and under room light. The maximum 8-hour period under room temperature and room light conditions for nivolumab injection in IV bag includes the product administration period (60 minutes). Vials of nivolumab for injection do not contain preservatives or bacteriostatic agents and should be prepared as soon as possible prior to administration using aseptic technique. **Please refer to the current Investigator Brochure for details.** 

#### 9.8 Administration

Nivolumab should be administered as an IV infusion over 60 minutes +/- 10 min through a 0.2 to 1.2 micron pore size, low-protein binding polyethersulfone membrane in-line filter. Nivolumab is not to be administered as an IV push or bolus injection.

No incompatibilities between nivolumab injection and polyvinyl chloride (PVC), non-PVC/non-DEHP (di[2-ethylhexyl]phthalate) IV components, or glass bottles have been observed.

## 9.9 Agent Ordering and Agent Accountability

BMS will be providing, packaged and labeled nivolumab complying with applicable local laws and regulations and made available directly to the sites participating in the study. Each batch of nivolumab will be delivered along with complete information regarding manufacture and expiration dates.

## 9.10 Accountability and Destruction of Agent

The Principal Investigator (or an authorized designee) at each participating institution must maintain a careful record of the inventory of the Investigational medicinal product received using

the Drug Accountability Form. The study drug may be destroyed as per site's destruction policies and documentation of study drug destruction will be submitted to CRO, providing the following minimal standards are met:

- On-site disposal practices must not expose humans to risks from the drug.
- On-site disposal practices and procedures are in agreement with applicable laws and regulations, including any special requirements for controlled or hazardous substances.
- Written procedures for on-site disposal are available and followed. A copy of the procedures must be provided to CRO upon request.
- Records are maintained that allow for traceability of each container, including the date disposed of, quantity disposed, and identification of the person disposing the containers.
   The method of disposal, i.e., incinerator, licensed sanitary landfill, or licensed waste disposal vendor must be documented.
- Accountability and disposal records are complete, up-to-date, and available for CRO to review throughout the clinical trial period. If conditions for destruction cannot be met, please contact CRO. CRO to discuss with BMS.

It is the Investigator's responsibility to arrange for disposal of all empty containers, provided that procedures for proper disposal have been established according to applicable federal, state, local, and institutional guidelines and procedures, and provided that appropriate records of disposal are kept.

Study drug may be returned to BMS if requested by the Study Chair or Co-Chair.

#### 10. RESPONSE EVALUATION CRITERIA

#### 10.1 Common Terminology Criteria for Adverse Events (CTCAE)

The descriptions and grading scales found in the revised NCI Common Terminology Criteria for Adverse Events (CTCAE) version 4.03 will be utilized for AE reporting. All appropriate treatment areas should have access to a copy of the CTCAE version 4.03. A copy of the CTCAE version 4.03 can be downloaded from the CTEP website (http://ctep.cancer.gov).

## **10.2** Response Criteria for Patients with Solid Tumours

See the table in *Section 8* and *8.2* for the schedule of tumour evaluations. In addition to the scheduled scans, a confirmatory scan should be obtained 28 days following initial documentation of objective response.

Response and progression will be evaluated in this study using the modified Response Evaluation Criteria in Solid Tumours (RECIST 1.1) for immune-based therapeutics guidelines deemed iRECIST (Seymour, 2017). Immunotherapeutics may result in infiltration of immune cells leading to transient increase in the size in malignant lesions, or undetectable lesions becoming detectable ('pseudo-progression'). The criteria are identical to those of RECIST 1.1 (Eisenhaur, 2009) in many respects but have been adapted to account for instances where an increase in tumour burden, or the appearance of new lesions, does not reflect true tumour progression.

RECIST 1.1 will continue to be used to define whether tumour lesions, including lymph nodes, are measurable or non-measurable, as well as for the management of bone lesions, cystic lesions, and lesions with previous local treatment and the method of measurement (Eisenhaur, 2009). The principles used to establish objective tumour response are largely unchanged from RECIST 1.1. The major change from RECIST 1.1 is the concept of resetting the bar if progression is followed at the next assessment by tumour shrinkage (Seymour, 2017).

